8 STUDY ASSESSMENTS AND PROCEDURES

8.1 EFFICACY ASSESSMENTS

The authors will conduct a comparative two-arm study investigating outcomes of second intention healing versus porcine xenograft placement of post-operative Mohs surgery or excision wound defects.

This will be a randomized evaluator blinded study with a prior power analysis. Basic demographic data will be obtained including date of birth, sex, and race. Medical record number will be retained to obtain phone number or address for patient call back should patient not show for their follow-up appointments.

Surgical defects 8 mm in diameter or larger on the lower extremities will be eligible for enrollment. Only patients with one wound will be eligible for enrollment. Primary intention (also known as linear layered) repair is not feasible in many patients with defects on the foot, ankle, or distal extremity as these are sites under high tension and poor circulation. Patients with small post-op defects many also opt not to be sutured via primary intention to avoid physical activity restrictions due to the increased risk of wound dehiscence. When closed via primary intention, a 0.8cm defect results in a scar of greater than or equal to 2.4cm.

Patients will be randomized to either receive a porcine xenograft or allow the wound to granulate via second intention. If primary/linear repair is not an acceptable option, the standard of care at Northwell is to allow the wound to heal on its own via second intention post-operatively. Due to recently published retrospective studies, there is a suggestion that porcine xenografts may be a feasible alternative to second intent healing. Currently, it is the surgeon's (and patient's) choice, after a discussion of risks and benefits of each modality, what is done.

Prior to intervention the defect size will be measured in terms of length and width using a sterile ruler.

After procedure completion wound care instruction will include daily dressing changes and application of petroleum jelly using a cotton tipped applicator to the wound daily until it is healed.

Weekly questionnaires will be given to the patients by phone or email follow-up until 12 weeks postsurgery.

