9.4.3 ANALYSIS OF THE SECONDARY ENDPOINT(S)

Analysis of all secondary endpoints will be considered exploratory. Thus, the analysis of secondary endpoints is not dependent on findings of the primary endpoint, and no adjustments for multiplicity will be made.

1. **POSAS patient scale total score.** Study participants will complete the POSAS patient scale at the 3month follow-up visit. The POSAS patient scale consists of 6 items assessing patients' subjective opinion of scar quality in terms of pain, itching, color, pliability, thickness, and relief. Each item is scored from 1 (normal pigmentation, no itching, etc.) to 10 ("worst imaginable scar or sensation"). The total score of the POSAS patient scale is calculated as the sum of the six items (range, 6-60).

2. **Healing time.** Healing time will be measured in weeks based on patient's responses to question 1 of the weekly follow-up questionnaire ("Is the wound completely healed (i.e., wound is completely closed with no open areas)?"). For example, a patient who first replies "Yes" to this question on the third weekly follow-up questionnaire will be assigned a healing time of 3 weeks. A more objective measure of healing time would not be feasible given our resources and patient schedule.

3. **Ratio of scare size to initial defect size**. The initial postoperative defect size will be measured by the investigator prior to intervention in terms of length and width using a sterile ruler. Initial defect area will be calculated as length times width. Scar size will be measured in terms of length and width at the 3-month follow-up visit, and scar area will be calculated as length times width. The outcome will be calculated by dividing the scar area by the initial defect area.

4. **Pain score at 1 week following surgery.** Patients' pain scores will be measured based on their response to question 2 of the weekly follow-up questionnaire. Patients will be asked to rate their current pain level at the operative site on a scale from 1 (no pain) to 10 (worst imaginable pain).

5. **Number of weeks with pain score above 1.** Patients' pain scores will be measured based on their response to question 2 of the weekly follow-up questionnaire. Patients will be asked to rate their current pain level at the operative site on a scale from 1 (no pain) to 10 (worst imaginable pain).

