9.4.4 SAFETY ANALYSES

Safety Endpoints:

1. **Infection.** Patient's charts will be reviewed at the completion of their 3-month office visit follow-up in order to analyze if they visited the dermatologist between the date of surgery and 3-month office visit and if infection was diagnosed.

2. **Bleeding**. During each of the weekly follow-up questionnaires and during the 3-month follow-up visit, patients will be asked if they have experienced any post-operative bleeding that led to a visit to the physician (yes/no) and if there was any intervention performed by the physician to stop the bleeding (yes/no). Bleeding will be considered an adverse event if an intervention by a physician was required to stop the bleeding. The number and percentage of patients who experienced bleeding at any time during the 3-month follow-up period will be reported.

3. **Pain**. The proportion of patients with a pain score ≥ 6 at the operative site will be assessed at one week following surgery. This will be based on the patient's response to the weekly follow-up questionnaire, with scores ranging from 1 (no pain) to 10 (worst imaginable pain).

Statistical Analysis: We will report the frequency and proportion of patients experiencing each of the safety endpoints above, based on the Safety Population defined in Section 9.3. The proportion of patients experiencing each type of complication (infection, bleeding, pain) will be compared between porcine xenograft and second intention healing using Fisher's exact test.

In addition to the planned safety analysis at the completion of the study, one interim analysis will be conducted by the study statistician after 26 patients have been randomized and complete the final study visit at 3 months post-intervention. This is equal to approximately 50% of the planned enrollment goal of 50 patients. The purpose of this interim analysis will be to review the safety endpoints. There will be no formal stopping rule based on the statistical significance of the interim safety analysis. The principal investigator will alert the IRB immediately if there is any evidence or suggestion of a difference between treatment groups with regard to AEs or SAEs. Additional details on this interim safety analysis are included in Section 9.4.6.

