9.4.6 PLANNED INTERIM ANALYSES

One interim analysis will be conducted after 26 patients have been randomized and complete the final study visit at 3 months post-intervention. This is equal to approximately 50% of the planned enrollment goal of 50 patients. The purpose of this interim analysis will be to review the safety endpoints delineated in Section 9.4.4. The primary efficacy endpoint (Observer POSAS score) and all secondary endpoints will not be evaluated. Thus, the interim analysis will not impact the Type I error rate for the primary efficacy analysis.

The number and proportion of patients who experience each of the adverse events below will be summarized, and compared between study arms using Fisher's exact test. Definitions and assessment procedures for these endpoints have been described in Section 9.4.4.

- Infection
- Bleeding
- Pain score at the operative site > 6 at week 1 post-intervention

The number and proportion of patients who experience any serious adverse event (SAE), as defined in Section 8.3.2, will be summarized and compared between study arms using Fisher's exact test. Given the minimal risk associated with dermatologic surgery, we do not anticipate any serious adverse events [22].

The interim safety analysis will be performed by [name], the study statistician. The statistician will be blinded to the treatment groups. All data provided to the statistician will list the treatment group as "A" or "B". The results of the interim safety analysis will be presented to the Principal Investigator, [name], who will be unblinded to the groups corresponding to "A" and "B".

There will be no formal stopping rule based on the statistical significance of the interim safety analysis. The principal investigator will alert the IRB immediately if there is any evidence or suggestion of a difference between treatment groups with regard to AEs or SAEs.

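### The pain safety endpoint reads only the week-1 score, and no planned analysis shows the severity of the weekly pain scores collected from week 2 to week 12

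*Combined protocol and SAP*

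**What the plan says.** Section 9.4.4 of the combined protocol and SAP lists infection, bleeding and pain as the safety endpoints. For pain, the proportion of patients with a score of 6 or more "at the operative site will be assessed at one week following surgery". The interim list in 9.4.6 has the same time point with a different inequality: "Pain score at the operative site > 6 at week 1 post-intervention". Section 3 also has > 6.

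The data collected run much longer. Section 8.1 states: "Weekly questionnaires will be given to the patients by phone or email follow-up until 12 weeks postsurgery". Each questionnaire asks for current pain from 1 to 10.

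Two secondary endpoints in 9.4.3 draw on those answers: "Pain score at 1 week following surgery" and "Number of weeks with pain score above 1". Both are analysed in the mITT population, and 9.4.6 excludes all secondary endpoints from the interim review. The POSAS patient scale, completed at the 3-month visit, measures "subjective opinion of scar quality in terms of pain, itching, color, pliability, thickness, and relief", but only the sum of its six items is analysed.

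The other two safety endpoints have a longer window. Infection is taken from chart review between surgery and the 3-month visit, and bleeding is counted at any time in those three months. Section 9.4.8 rules out individual listings by measure and time point.

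**The concern.** Pain is a named safety endpoint, yet its safety analysis reads the first of 12 scheduled scores, while its two companion endpoints use the full follow-up. No reason is given for the shorter window. The protocol itself expects many wounds to be open well beyond week 1: it gives typical healing as within 12 weeks of surgery and says hypergranulation may begin at 6 to 8 weeks (Section 6.5.1).

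If one method produced more high pain after the first week, the safety tables at the interim and at the end would not show it. If one method merely moved high pain from week 1 to week 2, it would look better on this endpoint. The interim matters in particular because Section 10.1.6 places safety oversight with the study team at that review.

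**Working it through.** The plan gives no figure for this point to reproduce. The sample size in 9.2 is set on the primary endpoint and is not affected. The check is to trace every planned use of pain data.

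| Planned use | Time read | How severity enters | Population | At the interim? |
|---|---|---|---|---|
| Safety endpoint 3 (9.4.4, 9.4.6) | Week 1 | At or beyond a cut-off, yes or no | Safety | Yes |
| Secondary endpoint 4 (9.4.3) | Week 1 | Full 1–10 score | mITT | No |
| Secondary endpoint 5 (9.4.3) | All weeks | Only above 1 or not | mITT | No |
| POSAS patient total (9.4.3) | 3 months ± 1 month | Pain is one of six items in a 6–60 sum | mITT | No |
| Adverse-event records (8.3.4) | Throughout | Clinician's grade recorded | No severity table specified | Only the three listed events and SAEs are tabulated |

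**Share of scores.** Weeks 2 to 12 supply 11 of 12 scheduled scores (11/12 = 92%). None is summarised by severity. This measures data use, not bias.

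**Two example patients over 12 weeks.** A scores 2 in weeks 2–6 and 1 otherwise. B scores 9 in weeks 2–6 and 1 otherwise.

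| | A | B |
|---|---|---|
| High pain at week 1 | No | No |
| Week-1 score | 1 | 1 |
| Weeks above 1 | 5 | 5 |
| Maximum score | 2 | 9 |
| High on any week (either cut-off) | No | Yes |

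The planned questionnaire endpoints cannot tell A from B. A maximum or any-week summary can.

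**POSAS.** The pain item can move the total by at most 10 − 1 = 9 points out of 60 − 6 = 54, or one sixth, and it is not reported separately. Section 6.5.1 says the scale cannot be given while the wound is open, so it does not record pain during healing.

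**Population.** The mITT population (9.3) requires the 3-month visit, or a later healed assessment after rescue. Section 9.2 allows for 10% attrition, about 0.10 × 50 = 5 patients. A patient with a low week-1 score and severe pain at week 4 who then drops out is a pain non-event in the Safety Population and is absent from endpoint 5.

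**Interim.** It takes place once 26 patients have completed the final visit, at two to four months. Most of their weekly scores are already due by then, but only week 1 is read.

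**Illustration of size, on assumed rates only.** With an independent weekly chance p of a severe score, the chance of at least one in weeks 2–12 is 1 − (1 − p)^11:

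| Assumed p | Chance | Patients per 25 |
|---|---|---|
| 0.5% | 5.4% | 1.3 |
| 1% | 10.5% | 2.6 |
| 2% | 19.9% | 5.0 |
| 5% | 43.1% | 10.8 |

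The formula assumes no decline as wounds heal and does not remove patients already counted at week 1. It shows only that the answer depends on p, which the documents do not give.

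**Power of an any-week comparison.** Two-sided Fisher's exact test at .05 with 25 per arm, on assumed rates: 5% versus 20%, 20%; 5% versus 30%, 55%; 10% versus 30%, 31%; 10% versus 40%, 59%.

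**The case against.** A single prespecified early time point is a legitimate postoperative pain endpoint, and an any-week measure depends on how many questionnaires each patient returns. Both points stand. They are reasons to keep the week-1 endpoint and to report completion beside any addition.

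The plan also has other routes to late pain. All adverse events are recorded with severity, onset and resolution (8.3.4). The surgeon monitors safety from follow-up data (10.1.7). Any suggestion of a difference in adverse events goes to the IRB (9.4.4, 9.4.6). A pain score is taken if the intervention is discontinued (7.1). A diagnosed infection is counted over three months, and a slow, painful wound would lengthen healing time and add weeks above 1. So a reader might infer that late severe pain is never captured anywhere, but the documents do not support that. The gap is narrower: no specified analysis shows the severity of the later weekly scores. No rule makes a high weekly score after week 1 an adverse event, and no table by severity is planned.

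Three other strong readings also fail:

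- A reader might take the safety objective as promising a comparison over all of follow-up. Section 3 sets no time window for it.
- A reader might treat the xenograft rejection described in Section 2.2 as a source of late pain. That section presents it as beneficial, through better local blood supply, and goes on to cite reduced pain.
- A reader might quote the illustrative percentages as an expected number of missed patients. They rest on assumed rates. The complication rates that the documents do give (1.6% overall in 8.3.2, under 1% for infection in 2.3.1) are not pain rates and do not support them.

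**Conclusion.** The concern holds in limited form. At both the interim and the final analysis, the pain safety endpoint uses one of 12 weekly scores, and no planned analysis reports the severity of the other 11. Endpoint 5 keeps only whether a score exceeds 1, in a population that leaves out patients who do not reach the final assessment. The POSAS pain item is absorbed into a total. This rests on the text alone and needs no assumption.

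How many patients would be affected is unknown, because the documents give no rate of late severe pain. The gap does not touch the primary analysis or the sample size. An added summary would be mainly descriptive, since formal comparison has low power at this size and lower still with 26 patients at the interim. The change is still worth making: it needs no new data and gives pain a window close to that of infection and bleeding.

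**What to change.** First reconcile the high-pain cut-off, which is ≥ 6 in 9.4.4 but > 6 in Section 3 and 9.4.6. A score of exactly 6 is an event under one and not under the other.

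Then keep the week-1 endpoint and add to 9.4.4 and 9.4.6, by arm in the Safety Population:

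- the number and proportion of patients reaching the reconciled cut-off on any weekly questionnaire through week 12 (at the interim, on those due by the data cut);
- the distribution of each patient's maximum score;
- the number of questionnaires answered, with patients who returned none shown separately.

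Label the summary descriptive. If a Fisher's test is attached, say that it has low power and that a non-significant result is not evidence of equal pain.

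The cost is a few lines of SAP text and one table from data already collected, with no change to sample size, visits or patient care. The downside is one more unadjusted safety summary, whose value depends on questionnaire completion.

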2.3 RISK/BENEFIT ASSESSMENT

2.3.1 KNOWN POTENTIAL RISKS

Second intention Healing:

Risk of infection, bleeding, scarring, numbness

Xenograft Placement:

Localized skin allergy: EZ-DERM Porcine Xenograft is latex-friendly and non-cytotoxic. Risk of slightly longer procedure: Application of the xenograft may increase the length of the procedure by up to 10 minutes. Risks of infection, bleeding, scarring, and numbness. Rates of infection followed skin surgery are less than 1%.

For Both:

Risk of Randomization: Your group might receive a less effective treatment and/or have more side effects than the other treatment group(s).

Risk of loss of confidentiality: There is a possibility that documents will be seen by individuals not included in this study. However, patient data will be stored in a password-protected electronic data capture tool in order to reduce the risk of loss of confidentiality.

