Block randomization will be used to ensure balance in the number of patients allocated to each treatment group. The randomization schedule will be uploaded to REDCap by a statistician outside of the study team. The PI, who will screen eligible subjects, will not have user rights for the Randomization Setup module within REDCap, and will thus be blinded to which treatment arm is next on the randomization list. Due to the nature of the treatment, it will not be possible to blind the patients. Patients will be asked not to inform the blinded physician observers which treatment they received. The PI will use the "Randomize" button within REDCap to assign patients to porcine xenograft or second intention healing after they have been consented and enrolled in the study.

Prior to intervention the defect size will be measured in terms of length and width using a sterile ruler.

After procedure completion wound care instruction will include daily dressing changes and application of petroleum jelly using a cotton tipped applicator to the wound daily until it is healed.

Weekly questionnaires will be given to the patients by phone or email follow-up. All complications and adverse events would be monitored and recorded for both study groups. Assessment of the scar will be blinded in nature.

The mode of treatment for participants will remain consistent throughout the 3-month period, as both methods are reliable for this type of defect. It is not general practice to place a xenograft on a wound healing by second intention or to remove a xenograft after one has been placed to switch to second intention. Should there be any complications, a modified intention to treat principle, described in Section 9, will be adhered to.

The scars for both study groups will be measured at a single follow up visit after 3 months \pm 1 month, and two blinded investigators will then assess the scar for the primary efficacy endpoint at this time. The blinded evaluators will be other MDs not involved in the study who are working in the dermatology department. The Principle Investigator will speak with the physician to outline what needs to be recorded for each patient. The validated physician observer scar assessment instrument (POSAS) will be used for this purpose. Scar size will consist of a length x width measurement using a ruler.

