7.2 PARTICIPANT DISCONTINUATION/WITHDRAWAL FROM THE STUDY

If patients decide to withdraw from the study, there is no danger involved with early withdrawal. Patients will be advised to follow up with the surgeon as normal standard of care outside the research setting.

Should patients wish to have their porcine xenograft removed following enrollment in the porcine xenograft arm or suffer from other complications resulting in porcine xenograft failure, they will be assessed in an intention to treat method.

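### The final safety analysis omits the by-arm SAE summary planned for the interim and has no count by arm of adverse events outside infection, bleeding and week-1 pain

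*Combined protocol and SAP*

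**What the plan says.** **End of study.** Section 9.4.4 lists infection, bleeding and week-1 pain, then states: "We will report the frequency and proportion of patients experiencing each of the safety endpoints above". The analysis set is the Safety Population, which 9.3 defines as everyone who receives the randomized intervention. The use of Fisher's test is restricted in the same way: "The proportion of patients experiencing each type of complication (infection, bleeding, pain) will be compared between porcine xenograft and second intention healing using Fisher's exact".

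**Interim.** Section 9.4.6 covers the same three endpoints and adds one item, an SAE summary by arm: "The number and proportion of patients who experience any serious adverse event (SAE), as defined in Section 8.3.2, will be summarized and compared between study". This takes place once 26 patients have completed the 3-month visit.

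**Collection.** Section 4.1 says: "All complications and adverse events would be monitored and recorded for both study groups". Section 8.3.4 puts every adverse event on a case report form whatever its relationship to treatment, and records SAEs until 30 days after the last day of participation.

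**Device-related events that the plan foresees.** Under xenograft placement only, 2.3.1 lists: "Localized skin allergy: EZ-DERM Porcine Xenograft is latex-friendly and non-cytotoxic". Section 7.2 allows for patients who have the graft removed or who "suffer from other complications resulting in porcine xenograft failure". Section 7.1 collects the reason and the specific complications when the intervention is discontinued.

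**Other places where a final table might appear.** Sections 9.4.7 (subgroups) and 9.4.9 (exploratory analyses) are marked as not applicable. Section 9.4.8 rules out individual listings by measure and time point. Section 10.1.6 ties safety oversight to the interim.

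**The concern.** The plan considers SAEs worth comparing by arm at about half of enrolment, but does not carry that comparison to the point where the data are complete. No reason is given for dropping it. An analyst who follows 9.4.4 would produce three rows and stop, and the only SAE comparison on file would be the interim one.

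The second gap is in non-serious events. A local allergic reaction that does not meet the seriousness definition would be on a case report form but in no planned table, at either look. That is the one reaction the plan attributes to the device alone. If someone tabulates such events later, the categories will be chosen after the data have been seen.

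At stake is how complete the safety description is in a small device trial. The primary endpoint, its alpha and its sample size are not affected.

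**Working it through.** **Inputs.** Planned total 50, 25 per arm (9.2). Interim at 26 completers (9.4.6). Allocation 1:1 (6.3). General complication rate 1.6% (8.3.2). Two-sided testing at 0.05 (9.4.1).

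**Assumptions.** (a) The interim SAE comparison is made on the 26 completers. Section 9.4.6 gives the trigger and does not define the data set separately. (b) The 26 split 13 and 13. The plan does not say so, and no block size is given. (c) All 25 per arm enter the Safety Population, which is the maximum. (d) The 1.6% is a general complication rate for dermatologic surgery, not an SAE rate, so it serves only as an illustration.

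**Step 1: coverage.** The plan calls the interim approximately 50% of enrolment: 26/50 = 52%, which agrees. The remainder is 50 − 26 = 24, and 24/50 = 48%. Patients lost before the 3-month visit are not completers and also fall outside. So can an SAE in an interim patient that arises after the data cut but within the 30-day window.

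**Step 2: what zero events would show.** The one-sided 95% upper bound for the event rate with no events in n patients is 1 − 0.05^(1/n).
- n = 13: 1 − 0.05^(1/13) = 20.6%
- n = 25: 1 − 0.05^(1/25) = 11.3%

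For a two-sided exact 95% interval, replace 0.05 by 0.025: the upper limits are 24.7% and 13.7%.

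**Step 3: chance of at least one event,** 1 − (1 − p)^n.

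| Assumed rate p | 13 in an arm | 25 in an arm |
|---|---|---|
| 0.5% | 6.3% | 11.8% |
| 1.6% | 18.9% | 33.2% |
| 5% | 48.7% | 72.3% |

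At 1.6% with both arms together: 34.3% in 26 patients, 55.4% in 50, and 32.1% in the 24 who are not covered.

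**Step 4: does the fuller set add power?** Against zero events in the other arm, the smallest split at which Fisher's exact test falls below 0.05 is 5 v 0 at 13 per arm (p = 0.039) and 6 v 0 at 25 per arm (p = 0.022). For rare events neither look has useful power. The gain is complete counts and tighter bounds.

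**The case against.** **The objective is already matched by its endpoints.** The objectives table in Section 3 sets the comparison of complication rates against infection, bleeding and pain, and 9.4.4 analyses those three. This stands. The mention in 2.2 of other post-surgical complications is background belief, not a hypothesis. A reader might infer that the plan fails its own complication objective, or that the final report will claim no difference in complications overall. The documents support neither: the objective is tied to the three endpoints, and no section plans such a conclusion.

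**Device reactions and graft problems are not wholly uncounted.** A reader might infer that allergy, hematoma, graft necrosis or dehiscence is never tabulated by arm. That is too strong. The interim SAE summary uses the definition in 8.3.2, which names several of these complications and can class an event as serious when it may need medical or surgical intervention. Cases meeting that definition would be in the interim SAE count. What has no planned count is the non-serious events, and SAEs outside the interim set.

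**Oversight continues.** Sections 9.4.4 and 9.4.6 require the principal investigator to alert the IRB to any suggested difference between arms in adverse events. Section 10.1.7 has adverse-event documentation reviewed after the fifth patient and then about every 20. These are safeguards, but none is a final table by arm.

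**SAEs are not expected and the trial is small.** Both are true: 9.4.6 anticipates none, and Step 4 shows that testing has little to offer. This is why the request is for description. The same expectation did not stop the plan from comparing SAEs at the interim.

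**Conclusion.** The point holds as a gap in the completeness of the planned safety reporting. On the text of 9.4.4 and 9.4.6, SAEs in about 24 of 50 planned patients (48%), and in anyone lost before 3 months, are in no between-arm comparison. Non-serious events outside the three endpoints have no planned final count by arm. The gap lies in analysis, not in collection.

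The practical size is modest: an upper bound of 20.6% rather than 11.3% when an arm has no events, and, at the illustrative 1.6%, a 19% rather than 33% chance of having at least one event in an arm to report. These figures rest on an even interim split and full treatment of 25 per arm. The 48% also rests on reading the interim set as the 26 completers; if patients still in follow-up at the cut were included, it would be smaller. The documents do not support reading this as a missed safety signal or as a threat to the primary result.

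**What to change.** In 9.4.4, make two additions to the end-of-study analysis, both on the full Safety Population:

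- Repeat the SAE summary of 9.4.6 by arm.
- Add one descriptive table by arm of patients with any adverse event and of adverse events by type. Include local allergic reaction in both arms, and xenograft removal or failure in the xenograft arm as recorded under 7.1. Give counts, percentages and exact 95% confidence intervals.

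Keep infection, bleeding and pain as the only formal comparisons among adverse-event types, so that no new tests are run on sparse rows.

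**Cost.** Mainly wording and one table, since 8.3.4 already captures the events. Two items need attention before the data are reviewed. The plan defines neither xenograft failure nor a local allergic reaction as an outcome, so a short working definition, and possibly a form field, is needed. The schedule of activities in 1.3 marks adverse-event review only at screening, whereas 8.3.4 has the investigator ask at each visit; these should be reconciled so that the table rests on the same ascertainment in both arms. The downside is a few sparse descriptive rows. Sample size, alpha and the primary analysis do not change.
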